6.2 Dose Modification

6.2.1 Dose-cohort Study Escalation/De-escalation and Stopping Rules Dose Level Determination

A recommendation to escalate to a higher dose cohort will only occur when the previous dose regimen(s) has/have been found to be reasonably tolerated based on available study data through study day 28 for all subjects and upon unanimous agreement of the DLRT members. Available data from previous cohorts will also be considered. Dose level recommendations will be made on a treatment cohort basis (not on an individual basis). After receiving the DLRT recommendation, Amgen will render a final decision

Protocol Number: 20200392

Date: 28 April 2022 Page 58 of 149

and will issue a written notification of the dose change decision to investigators. Further information on DLRM is provided in Appendix 3 (Section 11.3).

6.2.1.1 Dose-limiting Toxicity Evaluation Period

The minimum DLT evaluation period is defined as 28-days of treatment in cycle 1.

The DLT evaluation period may also be extended to assess events starting within the evaluation period in case the DLT definition is time dependent (neutropenia or thrombocytopenia, see below).

Subjects are considered DLT-evaluable if they experienced a DLT during the DLT evaluation period or if they received 75% of the planned doses of AMG 176 (and 100% of the planned doses of azacitidine in Part 2) and completed the DLT evaluation period.

Subjects who do not complete 75% of the planned doses of AMG 176 (and 100% of the planned doses of azacitidine) or discontinue from the study prior to completing the DLT evaluation period for reasons other than a DLT will be considered non DLT-evaluable for dose escalation decisions and OBD/MSBED determination and will be replaced by an additional subject at that same dose level. Subjects who receive supportive care during the DLT evaluation period that confounds the evaluation of DLTs (not including supportive care described in Section 6.2.1.2 as part of the DLT definition) may be considered non evaluable for dose escalation decisions and MSBED determination and replaced at the discretion of the Medical Monitor.

6.2.1.2 Definition of Dose Limiting Toxicities

A DLT will be defined as any of the events described below occurring in a subject during the DLT evaluation period and regarded by the investigators and/or Amgen Medical Monitor to be related to AMG 176. Any adverse event occurring outside the DLT evaluation period that is determined by the investigator to be possibly related to the investigational product, which is seen more frequently or is more severe than expected or is persistent despite appropriate management, can be determined to be a DLT upon unanimous decision by the DLRT after review of the adverse event and all available safety data. The grading of adverse events will be based on the guidelines provided in the Common Terminology Criteria for Adverse Events (CTCAE) version 5.0 (available online at http://evs.nci.nih.gov/ftp1/CTCAE/About.html). For troponin elevation, refer to Section 6.2.1.2.2 for CTCAE grading interpretation. Determination of the severity of adverse events will be consistent with CTCAE version 5.0. The relationship of an adverse event to investigational product will be determined by the Investigator. An event

Protocol Number: 20200392

Date: 28 April 2022 Page 59 of 149

should be considered related to treatment if, in the Investigator's medical judgment, there is a reasonable possibility that the event may have been caused by AMG 176.

6.2.1.2.1 Dose Limiting Toxicities

A DLT is defined as a grade 3 or higher non-hematological or a grade 4 hematologic adverse event that occurs during the DLT observation period (day 1 through day 28 after the administration of the first dose of AMG 176) in Part 1 unless clearly attributable to causes other than AMG 176 treatment.

If a DLT of TLS is observed during the lead-in period, it will be attributed to the lead-in period and a modification may be made to the lead-in period regimen for subsequent groups. Any other DLTs observed during the lead-in and/or designated group dosing period may require a modification of the designated cohort dose (and/or lead-in period regimen, if appropriate) as directed per the dose escalation guidelines.

Available study data, including data collected after the initial DLT-observation period along with demographics, investigational product administration, medical history, concomitant medications, adverse events, ECG, vital signs, laboratory results, and PK information will be reviewed. In addition to DLTs, all ≥ grade 3 toxicities not meeting DLT criteria will be reviewed and may be considered in DLRT decisions. Modeling of available potential safety risk data (eg, for thrombocytopenia) to predict safety risk for dose escalation decisions may also be considered.

Protocol Number: 20200392

Date: 28 April 2022 Page 60 of 149

Table 6-2. DLT Criteria

| | All Subjects |
|--------------|---|
| DLT Criteria | Non-hematologic adverse events: ≥ grade 3 non-hematologic adverse event that is not clearly resulting from the underlying leukemia recurrence within the DLT window of any adverse events listed under the non-hematologic adverse event exception (not including nausea and vomiting) any grade 2 non-hematologic adverse event lasting > 7 days that causes significant symptoms, dangerous medical repercussions, or warranting treatment interruption or dose reduction ≥ grade 3 nausea, vomiting or diarrhea persisting more than 3 days despite optimal medical support ≥ grade 3 fatigue persisting > 7 days any other ≥ grade 3 adverse event Failure to recover from AMG 176 related toxicities to grade ≤ 1 or baseline severity after delaying next cycle up to 14 days Hematological adverse events: Any grade 4 neutropenia and/or thrombocytopenia lasting ≥ 28 days from the start of cycle in the absence of active MDS or CMML Any treatment-related death Clinical TLS per Cairo-Bishop criteria (see Section 11.9.1) grade ≥ 3 not resolved to grade ≤ 2 within 7 days without end-organ damage Severe DILI per the Hy's Law criteria (ie, AST or ALT ≥ 3 x ULN and serum bilirubin > 2 x ULN measured on the same day, without signs of cholestasis and in absence of any other explanation for the DILI). See Section 6.2.3 for hepatotoxicity management. Grade 3 elevation of troponin-I (see grading criteria in Section 6.2.1.2.2)^a QTcF interval ≥ 501 ms or an increase of > 60 ms from baseline and Least 2 separate ECG assessments Asymptomatic, absolute decrease in LVEF of ≥ 10% from baseline AND LVEF < 50% Asymptomatic congestive heart failure |

Page 1 of 2

Footnotes defined on last page of the table

Protocol Number: 20200392

Date: 28 April 2022 Page 61 of 149

Table 6 2. DLT Criteria

| | All Subjects |
|------------|---|
| Exceptions | Infections and most hematologic adverse events Non-hematologic adverse events: grade 3 weight gain or loss grade 3 diarrhea despite optimal anti-diarrheal therapy that resolves to ≤ grade 2 within < 72 hours with or without clinical intervention grade 3 or 4 isolated electrolyte abnormalities that is not clinically significant and resolves to ≤ grade 2 within 72 hours with or without clinical intervention grade 3 nausea and vomiting that does not require tube feeding, total parenteral nutrition, or prolonged hospitalization and resolves to ≤ grade 2 within < 72 hours with or without clinical intervention grade 3 or 4 serum lipase without clinical signs or symptoms of pancreatitis that returns to baseline within 72 hours of interrupting study drug infection grade 3 (with concurrent neutropenia grade 3 or 4) that resolves to ≤ grade 2 within 7 days with or without clinical intervention grade 3 fatigue or asthenia grade 3 constipation that resolves to ≤ grade 2 within 7 days with or without clinical intervention |

AE = adverse event; AML = acute myeloid leukemia; ALT = alanine aminotransferase; AST = aspartate aminotransferase; CMML = chronic myelomonocytic leukemia; DILI = drug-induced liver injury; DLT = dose limiting toxicity; ECG = electrocardiogram; LVEF = left ventricular ejection fraction; MDS = myelodysplastic syndrome; QTcF = QT interval with Fridericia's correction; TLS = tumor lysis syndrome; ULN = upper limit of normal.

^a Further treatment with AMG 176 may be considered for grade 1 elevations of troponin-I after a cardiology evaluation is completed and results are discussed with the Amgen Medical Monitor.

Protocol Number: 20200392

Date: 28 April 2022 Page 62 of 149

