Number of DLTs No. of DLT-evaluable^a subjects treated at current dose Escalate Stay at current dose De-escalate^b 0 1 3 ≥ **2** 6 0-1 ≥ 2 9 0-1 2 ≥ 3 10^c 0-1 2-3 ≥ 4

Table 4-1. Guidelines for Dose Level Decisions in Part 1

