6.2.2 Dosage Adjustments, Delays, Rules for Withholding or Restarting, Permanent Discontinuation

For Hematologic Drug-Related Adverse Events (AE)

Dose reduction/interruption/discontinuation decisions should be based on the National Cancer Institute (NCI) CTCAE version 5.0 of the toxicity and the guidelines provided below. Dose modifications outside of those provided in Table 6-3 are allowable after discussion with the PI and documentation in the medical record, if in the best interest of the patient.

Patients with HR- MDS usually present with abnormal peripheral blood counts at the time therapy is started, and myelosuppression is an expected event during the course of therapy. Thus, no dose adjustments or treatment interruptions for myelosuppression will be planned in the presence of residual MDS. Dose-interruptions of azacitidine and AMG 176 in these patients should be considered on an individual case and discussed with the PI.

Protocol Number: 20200392

Date: 28 April 2022 Page 63 of 149

Patients with a response (with decline in blasts < 5%) who have prolonged (> 28 days) count recovery, may have the treatment with azacitidine and AMG 176 interrupted at the discretion of the treating physician after discussing with the PI until neutrophils recover to Absolute Neutrophil Count (ANC) is $\geq 500/\mu L$ and PLT to > $50 \times 10^9/L$. Investigators should, whenever possible, determine which medication is causing the toxicity and interrupt or dose reduce azacitidine and/or AMG 176, as applicable. After interruption, dose adjustment for azacitidine, AMG 176, or both can be made as follows:

- A reduction of two dose levels or holding of AMG 176 on day 22 may be considered
 if the myelosuppression or was deemed severe and life threatening by the treating
 physician, and if it is in the patient's best interest.
- If additional dose reductions are thought to be necessary by the investigator, a discussion with the PI or co-PI is required on an individual case.

For Non-Hematologic Drug-Related AEs

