6.2.2.1.5 Rules for Permanent Discontinuation

Subjects will permanently discontinue from the investigational product if the following are observed:

- Subjects experience adverse events meeting the DLT criteria at any time. Subjects
 will be followed until the DLT is resolved, returns to baseline value or is considered
 stable. Subjects will be withdrawn from AMG 176 treatment and will be treated as
 deemed appropriate by the investigator or treating physician. Except for:
 - Subjects showing evidence of response or subjects who in the opinion of the investigator may be responding to AMG 176, may have the option to continue therapy once the adverse events recover to baseline or grade 1 and the re-introduction of AMG 176 is deemed safe by the investigator, and Amgen's Medical Monitor. The subject should restart at a reduced dose.
- Intolerability of AMG 176.
- Grade 3 central laboratory elevations of troponin.
- Any Grade 4 arrhythmia possibly associated with AMG 176.
- Symptoms of clinically significant cardiac dysfunction (defined in Table 6-2), ECG changes, or diagnostic evidence of decreased cardiac function or cardiac injury irrespective of any cardiac troponin level (centrally or locally obtained). Study subjects that meet permanent discontinuation criteria require continuous cardiac monitoring (telemetry) for at least 24 hours, and a cardiologist evaluation that includes transthoracic echocardiography to assess the study subject and provide recommendations for further cardiac care. Monitoring should continue according to local SOC.
- Hepatotoxicity (as defined in Section 11.7).

The dosing is delayed > 4 weeks due to AMG 176-related adverse events.

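### Section 6.2.1.2.1 and Table 6-2 of the protocol define a hematologic DLT differently, neither is given precedence, and the same six subjects can count as 2/6 or 0/6

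*Protocol*

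**What the plan says.** Section 6.2.1.2 introduces the criteria inclusively: "A DLT will be defined as any of the events described below", provided that the event falls in the evaluation period and is judged related to AMG 176. Two descriptions of a hematologic DLT follow.

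- **Text of Section 6.2.1.2.1:** "A DLT is defined as a grade 3 or higher non-hematological or a grade 4 hematologic adverse event", in days 1 to 28 of Part 1, unless clearly attributable to another cause. It sets no minimum duration and no condition on disease status.
- **Table 6-2, criteria:** "Any grade 4 neutropenia and/or thrombocytopenia lasting ≥ 28 days from the start of cycle in the absence of active MDS or CMML".
- **Table 6-2, exceptions:** "Infections and most hematologic adverse events". The events covered by the word most are not listed.

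Three other places bear on which description is meant.

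- Section 6.2.1.1 lets the evaluation period be extended "in case the DLT definition is time dependent (neutropenia or thrombocytopenia, see below").
- Section 6.2.2 calls myelosuppression expected in these patients and says that "no dose adjustments or treatment interruptions for myelosuppression will be planned in the presence of residual MDS".
- Section 6.2.2.1.5 gives as a ground for permanent discontinuation: "Subjects experience adverse events meeting the DLT criteria at any time". It makes an exception for subjects who are or may be responding.

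The SAP (Section 5) defines the DLT observation period but not the DLT event, so it does not settle the question.

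**The concern.** A short grade 4 neutropenia judged related to AMG 176 is a DLT under the text and not a DLT under the table. Because myelosuppression is expected in this population, the two wordings part company in ordinary cases.

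The DLT count feeds three things in Part 1: the Table 4-1 guidelines, the mTPI rule in Appendix 14, and the 80% unacceptable-toxicity rule in that appendix. It also affects the individual patient. An event that meets DLT criteria leads to withholding (Section 6.2.2.1.3) and normally to permanent discontinuation (Section 6.2.2.1.5), whereas Section 6.2.2 plans no interruption for myelosuppression while MDS persists. If the text governs, the same neutropenia attracts opposite instructions.

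**Working it through.** **Inputs**

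- Table 4-1 ("Table 4-1. Guidelines for Dose Level Decisions in Part 1"), repeated as SAP Table 3-1. At 6 evaluable subjects, 0 or 1 DLT means escalate and 2 or more means de-escalate.
- Appendix 14: Beta(1,1) prior; target DLT probability 0.2. A dose is unacceptable if Pr(p > 0.2 | data) exceeds 0.80, and that dose and all higher doses are then closed. At least 6 subjects must be treated before escalation.

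**Formula.** With x DLTs in n subjects the posterior is Beta(1 + x, 1 + n − x). By the binomial identity, Pr(p > 0.2) = Pr(Bin(n + 1, 0.2) ≤ x).

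**Reproducing the plan's row at n = 6**

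- x = 0: 0.8^7 = 0.210. Below 0.80; Table 4-1 escalates.
- x = 1: 0.210 + 7 × 0.2 × 0.8^6 = 0.210 + 0.367 = 0.577. Below 0.80; Table 4-1 escalates.
- x = 2: 0.577 + 21 × 0.2² × 0.8^5 = 0.577 + 0.275 = 0.852. Above 0.80; Table 4-1 de-escalates.

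At n = 6 the table and the 80% rule therefore change over at the same count.

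**Worked case.** Six evaluable subjects. Two have grade 4 neutropenia of 10 days, related to AMG 176, starting by day 18 and so over before day 28 (or occurring with active MDS or CMML). There is no other DLT.

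| Definition applied | DLTs | Table 4-1 | Pr(p > 0.2) | 80% rule |
|---|---|---|---|---|
| Section 6.2.1.2.1 text | 2/6 | De-escalate | 0.852 | This and higher doses closed |
| Table 6-2 | 0/6 | Escalate | 0.210 | Not triggered |

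**Conditions on the 0/6**

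- The timing matters. A 10-day episode that starts on day 19 is still present on day 28 (19 + 10 − 1 = 28). If the table's duration clause means still present 28 days after the cycle starts, such an episode in a subject without active disease could count under the table too.
- Table 6-2 also has an entry for any other event of grade 3 or higher. It stands before the hematologic heading, so I read it as non-hematologic. The cell's layout was flattened when the PDF was read.

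**Limits of the comparison**

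- The unit probability masses in Appendix 14 also differ between the two counts. For escalate / stay / de-escalate they are 0.97 / 2.24 / 0.82 at 2/6 (stay) and 3.47 / 0.85 / 0.08 at 0/6 (escalate). I do not rest the point on them, because the printed stay interval (0.25, 0.35) does not contain the 0.2 target.
- Table 4-1 does not follow the 80% rule everywhere. It says stay at 1/3 (Pr = 0.819) and at 3/10 (Pr = 0.839). Closure of a dose therefore comes from Appendix 14 alone, not from Table 4-1.

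**The case against.** The strongest reply is that the structure resolves the conflict. Table 6-2 sits inside Section 6.2.1.2.1, beneath the general sentence, and its exceptions make sense only if they qualify that sentence. Section 6.2.1.1 treats the neutropenia and thrombocytopenia definition as depending on time, which fits the table and not the text. The no-interruption policy in Section 6.2.2 points the same way. This is good evidence of intent, and I accept that Table 6-2 is the likelier definition.

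A reader might go further and infer that Table 6-2 plainly governs and the text is a slip. The documents do not establish that. Section 6.2.1.2 makes any event described below a DLT, which includes the text. The Amendment 1 summary says that hematologic DLT criteria were revised on FDA recommendation but does not show the resulting wording. Choosing the table adopts the less strict safety definition, so it should not rest on inference.

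A reader might also infer that under Table 6-2 the dose would simply have been raised. That is not supported either. Section 6.2.1.2.1 has the review team look at grade 3 or worse toxicities that are not DLTs, and allows modelling of risks such as thrombocytopenia. Section 6.2.1 requires a unanimous recommendation before escalation and leaves the final decision with the sponsor. The two neutropenias would be seen. These safeguards act on the dose decision, however, and leave the DLT count undefined.

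Finally, little now depends on the point. Part 2 did not enroll (SAP Section 3.1), there is no interim or primary analysis (SAP Sections 7.1 and 7.2), and no safety summary tables are planned (SAP Section 9.6.1). This stands and limits the consequence.

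**Conclusion.** The inconsistency is real: two definitions of a hematologic DLT in one section and no rule of precedence. In the worked case it moves the count from 2/6 to 0/6, the Table 4-1 guidance from de-escalate to escalate, and the posterior probability from above the 80% limit (0.852) to well below it (0.210). No event rate is assumed. The result rests on both episodes being judged related, on their resolving before day 28 or occurring with active disease, and on the reading of Table 6-2 given above.

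A reader might infer that a DLT was missed or that a dose decision in this trial was wrong. The documents contain no event data and do not support that. What is affected now is how the DLT listing (SAP Section 9.6.2) and the study report's account of the dose decisions can be read. DLT incidence is part of the Part 1A primary endpoint, and a listing, even an empty one, cannot be interpreted without knowing the definition behind it.

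**What to change.** 1. The sponsor confirms which wording the Amendment 1 revision intended and names one governing definition: Table 6-2, if confirmed.
2. Re-check every recorded grade 4 hematologic event in the DLT period against that definition. The adverse event and laboratory listings (SAP Sections 9.6.2 and 9.6.3) are not enough alone, because Table 6-2 turns on whether MDS or CMML was active. Use the marrow and disease-response data as well.
3. State in the study report, and with the DLT listing, which definition was applied, and report any call that changes.
4. If the protocol is amended again, replace the definition sentence in Section 6.2.1.2.1 with a cross-reference to the governing definition. If that is Table 6-2, reword its exception to cover hematologic adverse events other than those listed as DLT criteria.

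SAP Section 10 says that no protocol amendment is required, so items 1 to 3 carry the fix. The cost is a clinical re-check in what the SAP calls a limited number of subjects, plus a sentence in the report and a note to the listing. It needs no new data collection: SAP Appendix C shows that marrow and disease-response forms exist.

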- ^d Hospitalization for TLS monitoring and prophylaxis: All subjects will be hospitalized to monitor for TLS. Hospitalization will begin within 24 hours before the first dose of AMG 176 and continue until 24 hours post first AMG 176 dose. If the target dose is 180 mg/m² or higher, hospitalization will also be required within 24 hours before administration of the target dose on day 8 and will continue until 24 hours post administration. Hospitalization period can be increased per institutional standards or investigators discretion. Hospitalization for the purpose of TLS prophylaxis will not be captured as an SAE.
- e TLS Prophylaxis: See Protocol for prophylaxis requirements (see Section 11.9) including additional serum chemistry and hematology laboratory samples that must be collected within 24 hours prior to the first dose (see Section 8.4.3.2). Electrolyte values must be within normal range prior to AMG 176 dosing.
- f AMG 176 dosing: AMG 176 will be administered QW IV on days 1, 8, 15, and 22 on a 28-day cycle. A lead in dose of 120 mg/m² will be required if the target dose is 180 mg/m² or higher. AMG 176 will be infused over 2 hours (± 5 minutes). Clinical visits on dosing days can be scheduled ± 1 day; however, safety and PK evaluations must occur at indicated time points, including a return to clinic 24 hours after dosing for safety and PK evaluations.
- ^g Azacitidine dosing: refer to the prescribing information for full details. The standard dose and schedule for azacitidine is as follows: Azacitidine will be administered at a dose of 75 mg/m² IV or SC daily on days 1 to 7 of each 4-week cycle.
- h Safety Labs: Safety labs include chemistry, hematology, urinalysis, and coagulation analytes. See Protocol for the list of analytes (Table 11-1). Pre-dose safety labs are to be collected per the SOA and can be collected up to approximately 24 hours before treatment begins unless otherwise indicated (eg, TLS monitoring test).
 - CBC with differential (differential not required if WBC \leq 0.5 k/ μ L), at least once weekly for the 1st cycle, then every 2 to 4 weeks during cycles 2 to 6, and then every 4 weeks (\pm 14 days) thereafter as long as they are on study.
 - Serum chemistry profile at least once weekly for the 1st cycle, then every 2 to 4 weeks during cycles 2 to 6, and then at least every 4 weeks (± 14 days) during active treatment.

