Investigators should, whenever possible, determine which medication is causing the toxicity and interrupt or dose reduce azacitidine and/or AMG 176, as applicable. Dose reductions will be as per Table 6-3 recommendations. Dose reductions different than Table 6-3 are allowed if determined to be in the patient's best interest and rationale documented in patient record. The investigators will use their clinical judgment to determine whether toxicity is caused by azacitidine, AMG 176, or both. Dose reductions of one of the agents, or both, are allowed after discussion with the PI or co-PI and documentation in the medical record.

Protocol Number: 20200392

Date: 28 April 2022 Page 64 of 149

Table 6-3. Dose Adjustments for Non-hematologic AEs That Are at Least Possibly Related

| Grade | Occurrence | Dose Modification | | |
|--|-----------------------|---|--|--|
| 1 or 2 | Anytime | No dose reduction | | |
| 3 or 4 Persistent grade 2: consider similar dose adjustments if persistent and not responding to optimal management in the opinion of PI and treating physician | First and second time | Hold AMG 176 ± azacitidine. Resume AMG 176 ± azacitidine a prior dose if recovery to ≤ grade 1 occurs within 14 days. If toxicity persists for 15 to 28 days, hold therapy and resume azacitidine and AMG 176 at prior dose if recovery to ≤ grade 1 or resume AMG 176 ± azacitidine at ONE dose level below current dose if recovery to ≤ grade 2. | | |
| | Third and fourth time | Hold AMG 176 ± azacitidine. Follow until toxicity ≤ grade 2. Resume AMG 176 ± azacitidine at ONE dose level below current dose. | | |
| | Fifth time | Hold AMG 176 ± azacitidine. Follow until toxicity ≤ grade 2. Resume AMG 176 ± azacitidine at TWO dose levels below current dose. | | |

PI = Principal Investigator.

Other Modifications of Dose Schedules

- Further dose reductions can be made to prevent adverse events and keep clinically significant toxicities grade ≤ 2.
- Dose adjustments by more than one dose level at a time can be considered when judged in the best interest of the patient (eg, severe myelosuppression) when toxicity has resolved. The reason for this reduction will be discussed with the PI or co-PI and documented in the medical record.
- Treatment interruptions and dose modifications other than the ones mentioned above
 can be considered after discussion with the PI and proper documentation of the
 rationale. Dose adjustment/delay of only one of the agents is permissible if the toxicity

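### Table 6-2 makes grade 3 fatigue lasting more than 7 days a DLT and also exempts it, with no stated precedence; with one other DLT among six subjects, the label reverses the dose decision

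*Protocol*

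**What the plan says.** Protocol Section 6.2.1.2.1, Table 6-2, has a criteria row and an exceptions row.

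- The criteria row includes a general line, "≥ grade 3 non-hematologic adverse event that is not clearly resulting from the underlying leukemia", and a specific line, "≥ grade 3 fatigue persisting > 7 days".
- The exceptions row includes "grade 3 fatigue or asthenia", with no duration attached. Other exceptions in that row are time-limited. Diarrhea and nausea/vomiting must resolve in under 72 hours, and constipation reads "grade 3 constipation that resolves to ≤ grade 2 within 7 days with or without clinical intervention".
- Only one line connects the two rows. It makes a DLT of "recurrence within the DLT window of any adverse events listed under the non-hematologic adverse event exception", nausea and vomiting aside. It covers repeat events and does not rank the rows for a first event.

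The text of Section 6.2.1.2.1 above the table restates a general grade 3 or higher rule without mentioning exceptions. It also lets the Dose Level Review Team (DLRT) consider grade 3 or higher events that are not DLTs, which presupposes that DLT status is already settled.

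The DLT count enters Protocol Table 4-1, reproduced as SAP Table 3-1. At six evaluable subjects the rule is escalate with 0 or 1 DLT and de-escalate with 2 or more, with no stay option. Protocol Appendix 14 adds that a dose is unacceptable if the posterior probability that its toxicity exceeds the 0.2 target is above 80%. That dose and all higher doses are then closed.

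**The concern.** Grade 3 fatigue lasting, say, eight days satisfies a criterion and an exception at once, so two investigators following the table correctly could label it differently. Three things depend on the label.

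1. **The DLT count.** This is part of the Part 1 primary endpoint and the input to the dose decision.
2. **The subject's treatment.** Protocol Section 6.2.2.1.5 requires permanent discontinuation after an event meeting DLT criteria, unless the subject is or may be responding. An exempt event falls under Table 6-3 instead: "Resume AMG 176 ± azacitidine a prior dose if recovery to ≤ grade 1 occurs within 14 days".
3. **Evaluability, in some cases.** Under Section 6.2.1.1, a subject who falls short of 75% of planned AMG 176 doses "for reasons other than a DLT will be considered non DLT-evaluable for dose escalation decisions and OBD/MSBED determination and will be replaced". A subject with a DLT stays in the count whatever the dosing.

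**Working it through.** **Step 1: can the text be reconciled?** Three readings are possible.

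| Reading | Consequence |
|---|---|
| Exceptions always prevail | The 7-day criterion has no effect for grade 3 fatigue, and the recurrence line is cancelled |
| Criteria always prevail | The general grade 3 or higher line swallows the non-hematologic exceptions |
| The duration-specific criterion limits the exception | Both fatigue lines have effect: exempt up to 7 days, a DLT beyond |

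The third reading is coherent and fits the neighbouring exceptions. It is not written down.

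**Step 2: reproduce the plan's row for six subjects.** Inputs from Appendix 14 are a Beta(1,1) prior, intervals (0, 0.25), (0.25, 0.35) and (0.35, 1), target 0.2 and limit 80%. With x DLTs in n subjects the posterior is Beta(1+x, 1+n−x). The unit probability mass (UPM) of an interval is its posterior probability divided by its width. For the 80% rule, P(rate > 0.2) = P(Bin(n+1, 0.2) ≤ x).

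- 1/6: 0.8⁷ + 7(0.2)(0.8⁶) = 0.210 + 0.367 = 0.577
- 2/6: 0.577 + 21(0.2²)(0.8⁵) = 0.577 + 0.275 = 0.852

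| DLTs | UPM escalate | UPM stay | UPM de-escalate | P(rate > 0.2) | Decision |
|---|---|---|---|---|---|
| 1/6 | 2.220 | 2.111 | 0.360 | 0.577 | Escalate |
| 2/6 | 0.974 | 2.241 | 0.819 | 0.852 | De-escalate |

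At 2/6 the UPM alone says stay, but 0.852 is above 0.80, so the dose is unacceptable. The printed row reproduces. It is the only row of Table 4-1 in which one more DLT goes straight from escalate to de-escalate. Six is also the smallest number at which Appendix 14 permits escalation.

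**Step 3: how often would one disputed event matter at six?** Given one such event, the decision turns only if exactly one of the other five subjects has an undisputed DLT. That probability is 5p(1−p)⁴, where p is an assumed undisputed DLT rate:

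- p = 0: 0
- p = 5%: 0.204
- p = 10%: 0.328
- p = 20%: 0.410

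**Step 4: how often would the readings differ at all?** The documents give no fatigue rate. Let d be an assumed per-subject probability of related grade 3 fatigue lasting more than 7 days with no other DLT. The share of six-subject cohorts in which the decision differs is P(Bin(6, p) ≤ 1) − P(Bin(6, p+d) ≤ 1), taking all six subjects as evaluable under both readings.

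| Assumed p | d = 1% | d = 2% | d = 5% |
|---|---|---|---|
| 0 | 0.15% | 0.57% | 3.3% |
| 10% | 2.0% | 4.1% | 10.9% |
| 20% | 2.5% | 4.9% | 12.1% |

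With p = 0 the difference comes only from cohorts with two or more disputed events.

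**Step 5: evaluability.** The Schedule of Activities footnote states "AMG 176 will be administered QW IV on days 1, 8, 15, and 22 on a 28-day cycle", which gives four doses. One missed dose leaves 3/4 = 75%, which still qualifies. Two missed leave 2/4 = 50%, which does not. So only a hold covering two or more doses makes the subject a counted DLT under one reading and a replaced subject under the other. An event starting after the day 15 dose can affect day 22 only.

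**The case against.** The strongest reply is that an experienced reader would not be in doubt. A specific line ordinarily qualifies a general one, and after the duration-specific lines Table 6-2 adds a catch-all for any other grade 3 or higher event. Table 6-2 also makes some grade 2 non-hematologic events lasting more than 7 days DLTs, including those that warrant a treatment interruption. It would be odd to exempt a worse event of the same duration. This stands as evidence of intent, and it supports the same fix. It does not supply the missing rule, because the heading of the exceptions row, read plainly, overrides the criteria.

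The second reply is that little turned on it. Fatigue is not among the identified risks in Protocol Section 2.3.2. Section 2.2.2.4 reports no DLTs at the recent dose reviews of the first-in-human study. The DLRT reviews all grade 3 or higher events, and escalation needs unanimity. These safeguards can block an escalation. They do not decide whether an event is a DLT, whether a subject is replaced or whether treatment stops.

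The third reply is that the study closed early. The SAP plans no primary analysis (Section 7.2) and no safety summary tables (Section 9.6.1), and related events are listed whatever their DLT label (Section 9.6.2). This limits the remaining use to the DLT listing and the study report's account of Part 1.

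The tension between permanent discontinuation in Section 6.2.2.1.5 and resumption under Table 6-3 exists for other grade 3 events too. The fatigue overlap does not create it; the label only decides whether the discontinuation rule applies.

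**Conclusion.** The point holds as a gap in a decision rule: the same event has two labels and no written rule chooses between them. At six subjects with exactly one other DLT, the label takes the result from 1/6, escalate, to 2/6, de-escalate and past the 80% limit. It also decides whether the discontinuation rule applies and, if at least two of the four weekly doses are missed, whether the subject is counted or replaced.

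The impact is conditional. The event must be regarded as related to AMG 176, and with no other DLT a single event leaves the six-subject decision unchanged. Every frequency in Steps 3 and 4 rests on assumed rates. The overlap concerns grade 3 only, since the exception covers no higher grade.

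A reader might infer that the table cannot be applied under any reading. It can: the third reading in Step 1 works, but it needs to be written. A reader might also infer that a dose decision in this trial was wrong. The documents do not support that, because they report no such fatigue event and do not say which reading the DLRT used.

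**What to change.** Extend the exception so that "grade 3 fatigue or asthenia" is followed by: *that resolves to grade 2 or lower within 7 days*. This complements the 7-day criterion and matches the neighbouring exceptions. The criterion names fatigue only, so grade 3 asthenia lasting longer would fall under the general grade 3 or higher line.

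For the closed study, keep the DLT labels that the DLRT used in the SAP Section 9.6.2 listing. Relabelling events afterwards would make the listing disagree with the decisions it documents. Only if a related grade 3 fatigue or asthenia event lasting more than 7 days occurred, state in the study report which reading was applied and whether the other would have changed the dose decision.

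The cost is one phrase in one table line, plus the usual IRB/IEC submission if the protocol is amended. For the closed study it is at most a short statement in the report. No new data, visits or subjects are needed.
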